3.4 ELIGIBILITY VISIT DESCRIPTION AND DATA FLOW

1. Prepare the EV1 and EV2 items before the applicant arrives. Place labels on all the forms.
2. Greet the applicant and give a brief description of what will be done at this visit. Answer any questions he/she may have. Collect all the medications brought in at EV1 and ask the participant if he/she has left any medications at home.
3. Give the participant the consent form before he/she begins Part 1 of EV1. Have him/her read it and sign on the bottom. The signing must be witnessed by one other person. Have the witness sign the consent form after the applicant has signed.
4. All forms should be reviewed for completeness by the study coordinator and given to the data entry person for further editing when the DES is made available.
5. Pages 1 - 4 of the Telephone Screening Form will be entered for all applicants.
6. All pages of EV1 and EV2 forms will be entered for all patients who are randomized into the study.

3.4.1 Eligibility Visit 1 (EV1)

3.4.1.1 Purpose

1. To answer additional questions the applicant may have about the study.
2. To have the participant complete Part I (Questions #1-21) of the EVI Form.
3. To have the interviewer complete Part II (Questions #22-64).
4. To determine continued eligibility and complete general medical condition questionnaire.
5. To determine alcohol consumption and rule out people who drink more than 5 drinks in a week.
6. To obtain a list of current physician-prescribed and self-prescribed medications.
7. To measure weight and height and compare against upper weight limit table.
8. To determine if there are any medical, personal, or professional reasons that would keep an applicant from participating in DELTA.
9. To determine women's menstrual status.
10. To measure blood pressure.

11. To measure fasting cholesterol by fingerstick method (using Cholestech machine) and Insulin by venepuncture.
12. To schedule EV2 if patient remains eligible.

[figure not shown]
3.4.1.2 Items Needed for EV1

1. EV1 questionnaire to be completed by the interviewer.
2. Blood pressure cuff.
3. Cholestech Machine and cassettes.
4. Collect medications from applicant to verify medicines.

3.5 PHYSICAL MEASUREMENTS

3.5.1 Standing Body Height

The participant stands erect on the floor or the horizontal platform with his/her back against the vertical mounted metal centimeter ruler, heels together and against the vertical ruler, looking straight ahead with his/her head in the Frankfort horizontal plane (the horizontal plane which includes the lower margin of the bony orbit -- the bony socket containing the eye -- the most forward point in the supratragal notch -- the notch just above the anterior cartilaginous projections of the external ear) (Figure 1). The right angle is brought down snugly but not tightly on the top of the head. A foot stool is used if the examiner is shorter than the participant such that the examiner's view is level with the point of measurement on the head of the participant. The participant's height is recorded to the centimeter or inch, rounding down.

ORBITAL:	Lower margin of eye socket
TRAGION:	Notch above tragus of ear or at upper margin of zygomatic bone at that point
FRANKFORT PLANE:	Orbital-tragion line horizontal

Figure 3.5.1.1: Frankfort Plan or Measuring Body Height

Figure 3.5.1.2: Body Weight Scales Calibration Form

BODY WEIGHT SCALES CALIBRATION FORM

- A) **DAILY:** At the beginning of each day, scales should be checked to see that they read zero when there is no weight on them.
- B) **WEEKLY:** Calibrate the scales using the 50 pound known weight. This calibration is performed again whenever the scales are moved. If the scales are outside the 49.5 to 50.5 range an independent service technician is called in to recalibrate the scales. Calibration with the 50 pound weight is performed for both balance arms (light and heavy) on the scale.
- C) **ANNUALLY:** The scales are certified annually by an independent scale technician.

The Anthropometry Equipment Calibration Form should be filled out and sent to the Coordinating Center bi-weekly.

1. Calibration Check of Scales with 50 lb weight			Initials: _____
Reading of scales with 50 lb weight _____			
If reading is outside of 49.5 to 50.5 range, scale should be serviced.			
If service is requested, give		Date ____-____-____	
Recalibration by independent service technician		Technician: _____	
2. Repeat Calibration because of moving of scales			
Scales moved:	1. Date ____-____-____	2. Date ____-____-____	
	Initials _____	Initials _____	
Calibration:	1. Date ____-____-____	2. Date ____-____-____	
	Initials _____	Initials _____	

Today's Date ____-____-____

Completed by _____

Center _____

3.5.2 Body Weight

Before a participant is weighed, the scale is balanced so that the indicator is at zero when no weight is on the scale. The scale must be level and on a firm surface (not a carpet). The participant is instructed to stand in the middle of the platform of the balance scale with head erect and eyes looking straight ahead. Adjust the weight on the indicator until it is balanced. Record the results down to the pound or kg, rounding down. To maintain accuracy, the scale is zeroed daily and must be calibrated with a known weight (50 lbs.) every week or whenever the scale is moved.

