Question 43-47: Body Mass Index (BMI)

Complete either questions 43 & 44 or 45 & 46 based on whether your Field Center will be using customary or metric units of measure.

43. a. & b. Enter the applicants height in feet and inches. Height should be without shoes rounded to the nearest inch.
44. a. Enter applicant's weight in pounds. Weight should be without shoes and rounded to the nearest pound.
b. Find the applicant's height in the BMI table provided, check the information, and circle YES or NO.

OR

45. Enter the applicant's height in centimeters. Height should be without shoes and rounded to the nearest centimeter.

46. a. Enter the applicant's weight in kilograms. Weight should be without shoes and rounded to the nearest kg.
- b. Find the applicant's height in the BMI table provided, check the information, and circle YES or NO.
47. Circle YES or NO. (UNSURE is not a response option for this question.)

NOTE: If the applicant's weight is greater than the upper weight limit, or the applicant is not willing to maintain the same weight, then the applicant has become ineligible. If so, thank the applicant for his/her time and interest, and terminate the interview.

Questions 48-54: Sitting Blood Pressure

48. Measure the applicant's arm circumference in centimeters and record this value in the space provided.
49. Select the appropriate cuff size and circle the corresponding letter (e.g.: if a applicant's arm is 31 cm circle R for regular adult size.)
50. Obtain pulse obliteration value by inflating cuff until pulse can no longer be heard. Add 30 to this value to obtain peak inflation level and enter the sum in Part b.
51. Obtain the applicant's 30 second pulse, record this value in the left most space provided, multiply by 2, and enter the product in the right most space provided.

After applying the blood pressure cuff, the applicant must sit quietly and remain seated with legs uncrossed for 5 minutes before the blood pressure measurements are obtained.

52. a.-b. Record both the systolic and diastolic values for the first blood pressure measurement in the appropriate spaces.

Wait 30 seconds after the first blood pressure reading before taking the second reading.

53. a.-b. Record both the systolic and diastolic values for the second blood pressure measurement in the appropriate spaces.

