4.5 PARTICIPANT WEEKLY MONITORING

Figure 4.5.1

Instructions for Completing the Participant Weekly Monitoring Form

Note that questions 7-13 on this form are asked at the first weekly interview concerning the participant's activity during the previous week.

Data from this form will be entered into the data management system.

DELTA ID

Apply the pre-printed DELTA ID label or write in the 5-character ID number.

Monday's Date

Enter the current Monday's date which is usually the first day each week that a participant is interviewed. Enter the date as month/day/year using leading zeros to fill in all spaces.

Question 1: Personnel Code Number

Record the personnel code number assigned to the DELTA study staff for the person completing this form.

Questions 2-4: Blood Draw

These items are completed only during weeks 5, 6, and 7.

2. Circle the number of the Feeding Period.
3. Circle the number of the week into the Feeding Period.
4. Fill in the specific date of the blood draw. Enter the date as month/day/year using leading zeros to fill in all spaces.

Questions 5-6: Weight

The participant will be interviewed twice each week, usually on Monday and Thursday, to record weight and other vital information.

- 5a-d. Enter the date, weight, and current calorie level from the first weekly interview, usually on Monday. In 5a, enter the date as month/day/year using leading zeros to

fill in all spaces. In 5b or 5c, record the participant's current weight either in pounds (lbs) or kilograms (kg), respectively. Weigh the participant before the dinner meal, without shoes or coats. In 5d, circle the calorie level based on the body weight in 5b or 5c. The calorie level is adjusted such that the participant's weight does not vary 2.2 pounds (1 kg) or more than the target weight. (*Note to the Interviewer: For target weight, use the weight recorded on the first day of feeding period 1 or the first weekly weight recorded during the first week of feeding period 1.*)

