5.4.6 Energy Adjustment

Adjustments in the calorie level may be made after the run-in period based on the participant's perception of whether the amount of food is too much or too little. Thereafter, adjustments will be made based on body weight monitoring. See weekly monitoring (PWM) form. Participants should remain on the initial calorie level for about one week before adjusting calories unless they are unusually hungry or full.

Menus are calculated at 5 standard calorie levels 1500, 2000, 2500, 3000 and 3500. If the participant's weight varies ≥ 1 Kg. (2.2 lbs) from the baseline weight, the calorie level is lowered or raised accordingly.

Weight gain in premenopausal women is evaluated in relation to the menstrual period. If weight gain occurs during the menstrual period, reduction in energy intake should be made only if the weight gain persists one week after the menstrual period.

5.4.7 Adjusting calories in feeding periods 2 and 3

Participants will be given guidelines for eating between feeding periods (see section 5.12) and cautioned to maintain their weight. Participants should be placed on the same calorie level they stabilized at during feeding period 1 and allowed to fluctuate during the first two weeks, before making adjustments.

Figure 5.4.7.1: DELTA Menu Schedule - Protocol 2

***Feeding Period 1
Menu Schedule for DELTA - 2
SEPTEMBER, 1994***

SUN	MON	TUE	WED	THU	FRI	SAT
				[1]	[2]	[3]
[4]	[5]	[6]	[7]	[8]	[9]	[10]
[11]	[12]	[13]	[14]	[15]	[16]	[17]
[18]	[19]	[20]	[21]	[22]	[23]	[24]
[25]	[26]	[27]	[28]	[29]	[30] Begin (2) cycle 1	

Menu Schedule for DELTA - 2 OCTOBER, 1994

SUN	MON	TUE	WED	THU	FRI	SAT
						[1] W1 cycle 1
[2] W2 cycle 1	[3] 3 cycle 1	[4] 4 cycle 1	[5] 5 cycle 1	[6] 6 cycle 1	[7] 1 cycle 2	[8] W3 cycle 1
[9] W4 cycle 1	[10] 2 cycle 2	[11] 3 cycle 2	[12] 4 cycle 2	[13] 5 cycle 2	[14] 6 cycle 2	[15] W1 cycle 2
[16] W2 cycle 2	[17] 1 cycle 3	[18] 2 cycle 3	[19] 3 cycle 3	[20] 4 cycle 3	[21] 5 cycle 3	[22] W3 cycle 3
[23] W4 cycle 3	[24] 6 cycle 3	[25] 1 cycle 4	[26] 2 cycle 4	[27] 3 cycle 4	[28] 4 cycle 4	[29] W1 cycle 4
[30] W2 cycle 4	[31] 5 cycle 4					

Menu Schedule for DELTA - 2 NOVEMBER, 1994

SUN	MON	TUE	WED	THU	FRI	SAT
		[1] 6 cycle 4	[2] 1 cycle 5	[3] 2 cycle 5	[4] 3 cycle 5	[5] W3 cycle 5

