 - c) A "Take-Out Meal Request" will be completed and approved by both the nurse and the dietetic coordinators. (See attached).
 - d) For compliance assessment, a participant will be expected to return all food containers and uneaten foods to the metabolic kitchen.
 - e) Participants can take-out more meals than allowed only when approved by the PI, the nurse coordinator, and the dietetic coordinator. This procedure will allow for emergencies and for other special cases.

Figure 5.9.5.3 Take Out Meal Request (PBRC)

**TAKE-OUT MEAL REQUEST
PENNINGTON BIOMEDICAL RESEARCH CENTER**

(Participant name/ID) _____, enrolled in the
_____ study requests permission to take-out the following meals on the
dates specified below:

Date: _____	B	L	D	Snack
Date: _____	B	L	D	Snack
Date: _____	B	L	D	Snack

The meals should be ready by _____ (time) on _____ (date).

(Participant name/ID) _____ has been informed of
his/her responsibility for handling the food in a prudent manner to assure food safety.
He/She also has been told to return the empty food containers and any uneaten foods to the
metabolic kitchen for compliance assessment.

Study Coordinator

Date

Dietetic Coordinator
Date

Figure 5.9.5.4 Columbia Policy for Special Request Packed Meals

Columbia Policy for Special Request Packed Meals

Dear DELTA Participant,

The first weekend of the DELTA study is just around the corner. We will be packing the following meals for you:

Saturday's - Breakfast
Lunch
Dinner
Snack

Sunday's - Breakfast
Lunch
Dinner
Snack and

Monday's - Breakfast
Lunch

You are allowed to eat only one meal on your own with our guidelines.

THE "FREE" MEAL COULD BE EATEN AS DINNER IN PLACE OF SATURDAY'S LUNCH OR SUNDAY'S LUNCH.

Please let us know by Wednesday each week if you are planning to eat on your own.

WEEKDAY TAKE-OUT MEAL GUIDELINES

1. You may take-out 1 "one-site" meal during each diet period.
You must request 3 days ahead of time for the take out-meal to [name] or [name].
2. It is your responsibility to keep the food safe.

PLEASE REFRIGERATE THE FOOD IMMEDIATELY.

Please bring empty containers on Monday or the following day.

Please complete the 'PACKED MEAL FORMS' and give it back to the DELTA Staff.

All of you will be given food records for the weekend. On these food records please write down everything you eat and drink on Saturday and Sunday, and return it to us when you come for your lunch on Monday. We will weigh you every Monday and Thursday before lunch.

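### Body weight is recorded in whole pounds or kilograms, which is too coarse to apply the 1 kg (2.2 lb) limit for changing calorie level

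*Protocol*

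**What the plan says.** Section 3.5.2 gives the manual's only general procedure for weighing a participant, and its recording rule is: "Record the results down to the pound or kg, rounding down". The same section requires daily zeroing and weekly calibration of the scale.

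The weights that govern energy intake are taken twice a week under section 4.5, in pounds or kilograms. No recording precision is given there. The instruction is: "The calorie level is adjusted such that the participant's weight does not vary 2.2 pounds (1 kg) or more than the target weight". The reference is a single reading: "For target weight, use the weight recorded on the first day of feeding period 1 or the first weekly weight recorded" in the first week of that period. Section 5.4.6 repeats the limit: if weight differs by 1 kg or 2.2 lb or more "from the baseline weight, the calorie level is lowered or raised accordingly".

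Two other passages differ in detail. The Eligibility Visit 1 instructions (section 3.6, Question 46a) say: "Weight should be without shoes and rounded to the nearest kg". They also let each center choose metric or customary units. On timing, section 4.5 has participants weighed before dinner, while Columbia's letter to participants (Figure 5.9.5.4) says: "We will weigh you every Monday and Thursday before lunch".

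**The concern.** A limit of 1 kg cannot be read reliably from weights kept in 1 kg steps, because the step is as large as the limit. In whole pounds the limit of 2.2 lb falls between two recordable differences, so the effective limit moves up to 3 lb. The target carries the same rounding error, and because it is fixed from the start of feeding period 1 the error stays with the participant.

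Keeping weight constant is one of the controls the study depends on. Section 1.1.5 says the diets are designed to prevent weight change, and section 5.12 warns participants that a weight change could affect the results. What is at stake is whether one adjustment rule works the same way for every participant at every center.

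**Working it through.** **Inputs from the protocol.** Recording step: 1 kg or 1 lb, rounded down (3.5.2). Limit: 1 kg or 2.2 lb (4.5, 5.4.6). Reference: one recorded weight (4.5). Frequency: two weighings a week for 7 weeks.

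**The plan's own figure.** 1 kg = 2.2046 lb, so equating 1 kg with 2.2 lb is correct. The units agree; the recording step is the difficulty.

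**Formula.** Let w be the true weight when the target is set and d the true change. The rule triggers if |floor(w + d) − floor(w)| reaches the limit. Take the fractional part of w as uniform on 0 to 1.

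**Whole kilograms.** A recorded difference of 1 is enough, so P(trigger) = min(|d|, 1).

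**Whole pounds.** The smallest whole number that is at least 2.2 is 3. So P = 0 up to 2 lb (2 / 2.2046 = 0.91 kg), P = |d| − 2 between 2 and 3 lb, and P = 1 from 3 lb (3 / 2.2046 = 1.36 kg). At 1 kg, P = 2.2046 − 2 = 0.20.

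| True change (kg) | Whole kg | Whole lb |
|---|---|---|
| 0.1 | 10% | 0% |
| 0.5 | 50% | 0% |
| 0.9 | 90% | 0% |
| 1.0 | 100% | 20% |
| 1.2 | 100% | 65% |
| 1.36 | 100% | about 100% |

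A simulation of 1,000,000 starting weights between 60 and 110 kg gave the same values. Rounding to nearest gave the same probabilities, so the loss comes from the size of the step, not from the direction of rounding.

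**False triggers with no true change.** This part needs a day-to-day SD for a single weighing, which the protocol does not give. It is assumed here, and it applies to both the target and the later weight.

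| Assumed SD (kg) | Whole kg | Whole lb | 0.1 kg | Exact |
|---|---|---|---|---|
| 0.2 | 23% | 0% | 0.1% | 0% |
| 0.3 | 34% | 1% | 2.5% | 2% |
| 0.5 | 51% | 11% | 18% | 16% |
| 0.7 | 63% | 26% | 34% | 31% |

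These are rates per weighing. There are 2 × 7 = 14 weighings per period, but not all can lead to a change. Section 5.4.6 keeps participants on the initial level for about a week, leaving about 14 − 2 = 12. Section 5.4.7 lets weight fluctuate for the first two weeks of periods 2 and 3, leaving about 14 − 4 = 10.

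**Effect of finer recording.** At 0.1 kg the rule acts between 0.9 and 1.0 kg. At 0.25 lb the first recorded difference of at least 2.2 is 2.25 lb, so it acts between 2.0 and 2.25 lb (0.91 to 1.02 kg). Either band is far narrower than just above 0 to 1 kg (whole kg) or 0.91 to 1.36 kg (whole lb).

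**The case against.** The strongest reply is that section 3.5.2 sits in the chapter on eligibility visits. The weekly instructions in section 4.5 neither refer to it nor state a rounding rule of their own, and a limit quoted as 2.2 lb suggests that finer readings were expected. The calibration form (Figure 3.5.1.2) judges scales against 49.5 to 50.5 lb, so half-pound readings seem possible. This stands in part: applying 3.5.2 to weekly weights is an inference. It is the natural one, because the manual gives no other general weighing procedure and the weekly calibration duty points to use throughout the study.

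A reader might infer that some centers are in fact adjusting on noise in kilograms while others miss 1 kg changes in pounds. The documents do not support that. They do not say which center uses which unit for weekly weights, and if all used pounds the difference between centers would vanish.

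A reader might also infer that pound recording leaves drift uncorrected, or that diet effects on triglycerides, insulin or HDL are confounded. Neither follows. With pounds, triggering is certain at most 0.36 kg beyond the limit, and weight is checked twice a week. Each participant receives a sequence of diets, and the rounding rule does not depend on diet.

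It also stands that some false triggering would remain with exact weights (16% at SD 0.5 kg), because the target is a single noisy reading. The hold periods, the menstrual-period provision in section 5.4.6 and the 150 kcal unit foods in section 5.4.4 soften the effect. None of them restores the lost precision.

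**Conclusion.** The point holds: as written, the recording rule defeats the decision limit. If section 3.5.2 is followed for weekly weights, a true 0.5 kg change triggers half the time in whole kilograms and never in whole pounds. A true 1 kg change triggers always in kilograms and about 20% of the time in pounds. These figures assume only that the fractional part of weight is uniform. The false-trigger rates with no drift (34 to 51% per weighing in whole kilograms, against 2 to 16% with exact weights) rest on an assumed SD of 0.3 to 0.5 kg and are illustrative.

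The consequence is added noise, and uneven weight control wherever units differ between centers. It should be corrected because the remedy is simple.

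**What to change.** In section 3.5.2 and in the weekly monitoring instructions of section 4.5, state one finer recording precision for target and weekly weights at all centers, for example 0.1 kg or 0.25 lb as the scale graduations allow. Drop whole-unit rounding for these weights and compare the resulting difference with the existing limit. The adjustment rule itself stays as it is.

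Two inconsistencies should be reconciled separately: the time of weighing (before dinner in section 4.5, before lunch in Figure 5.9.5.4) and the rounding wording (down in section 3.5.2, nearest in section 3.6).

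The cost is a sentence or two in each place, and no new equipment if the scales are graduated finely enough. If they can be read only to half a pound, the rule would act between 2.0 and 2.5 lb (0.91 to 1.13 kg), which is still narrower than with whole pounds.

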3.5.3 Blood Pressure

3.5.3.1 Cuffs and Bulbs

Proper size of the cuff is essential for accurate blood pressure measurement. Field Centers have four standardized cuffs available - small adult, regular adult, large adult, and thigh cuff.

The range markings on commercial cuffs overlap from size to size and do not offer a precise guideline. In the DELTA study arm size is measured, and the cuff size is selected as follows:

Table 1. Determination of cuff size based on arm circumference

Cuff	Size	Arm Circumference
Small	Adult/Child	<24.5 cm
Regular	Adult	24.5-33.0 cm
Large	Adult	33-40 cm
Thigh		>40 cm

3.5.3.2 Blood Pressure Measurement Instructions

The Coordinating Center is presenting the ARIC procedure at this time in lieu of any final decisions on blood pressure measurements as endpoint determinations (pending Steering Committee decision). Some of the many extraneous factors influencing blood pressure are controlled by standardizing the measurement technique and the environment in which the measurement is made. Blood pressures should be taken before any attempts to draw blood.

3.5.3.3 Staff Preparation for Participant Visit

In relating to the DELTA participants, remember that participation in the study is voluntary. Participants are given full explanation and instructions about the preparation for the blood pressure examination and an opportunity for questions. The setting in which blood pressure measurements are made is standardized and takes place in a separate, quiet room where no other activity is taking place, and where temperature fluctuations are minimal. Clinic scheduling procedures establish consistent appointment times to minimize as much as possible the impact of daily blood pressure variation.

